### 12.6.3.2 Questionnaires

#### 12.6.3.2.1 FTND Questionnaire

The FTND questionnaire will be administered at Screening and the Day 90 Visit.

FTND score value and the number and percentage of subjects in each category (mild/moderate/severe) will be presented at Screening and Day 90 Visit. The change from Screening in the FTND score at Day 90 will also be presented. The changes in the categories will also be presented in a shift table.

All summaries and shift tables will be performed on the PP, FAS and Compliant populations.

The data will be presented in the below outputs:

TFL number	Title
TABLES	
15.2.1.4.1	Summary of Demographics and Other Baseline Characteristics – Safety Population
15.2.1.4.2	Summary of Demographics and Other Baseline Characteristics – FAS
15.2.1.4.3	Summary of Demographics and Other Baseline Characteristics – PP Set
15.2.1.4.3.1	Summary of Demographics and Other Baseline Characteristics by Sex – PP Set
15.2.1.4.3.2	Summary of Demographics and Other Baseline Characteristics by Cigarette Consumption – PP Set
15.2.4.51.1	Descriptive Statistics of Fagerström Test for Nicotine Dependence Results – PP Set
15.2.4.51.2	Descriptive Statistics of Fagerström Test for Nicotine Dependence Results – FAS
15.2.4.51.3	Descriptive Statistics of Fagerström Test for Nicotine Dependence Results – Compliant Population

TFL number	Title
LISTINGS	
15.3.6.13	Listing of Fagerström Test for Nicotine Dependence Results

### 12.6.3.2.2 Urge-to-Smoke Questionnaire of Smoking Urges Brief

The QSU-brief will be administered daily from Days -1 to 5, and Days 30, 60 and 90. The change from baseline will be calculated for the total score and the two domain scores (relief and reward). The total score and two domain scores, along with the percent change from baseline will be summarized. The answers to the individual questions, along with the domain scores, total scores, changes and percent changes from baseline will be listed.

The profiles of the raw means from baseline to Day 90 Visit for the total score and two domain scores will be produced.

The analysis will be performed separately for each post-baseline timepoint in the domain and total scores. An ANCOVA model will be used with terms for baseline QSU-BRIEF score, sex, average daily mCC consumption over the last 4 weeks as reported during screening, and randomization arm. No adjustment will be made for multiple comparisons. The SAS code to be used is similar to the model reported in Section 12.6.1.3 "Sensitivity Analysis", amended as appropriate to obtain the required comparisons.

LS means for each randomization\_arm along with the difference (THS 2.2 Menthol - mCC) and (THS 2.2 Menthol – SA) with 95% CI will be presented in the tables.

All figures, summaries and analyses will be performed on the PP Set and the FAS.

The data will be presented in the below outputs:

TFL number	Title
FIGURES	
15.1.2.4.1	QSU-brief Total Scores Arithmetic Mean and 95% CI – PP Set
15.1.2.4.2	QSU-brief Total Scores Arithmetic Mean and 95% CI – FAS
15.1.2.5.1	QSU-brief Total Scores Least Squares Means Differences and 95% CI – PP Set
15.1.2.5.2	QSU-brief Total Scores Least Squares Means Differences and 95% CI – FAS
TABLES	
15.2.4.52.1	Descriptive Statistics of QSU-brief Factors and Total Scores – PP Set
15.2.4.52.2	Descriptive Statistics of QSU-brief Factors and Total Scores – FAS
15.2.4.53.1	Analysis of QSU-brief Factors and Total Scores – PP Set
15.2.4.53.2	Analysis of QSU-brief Factors and Total Scores – FAS
LISTINGS	

TFL number	Title
15.3.6.14	Listing of QSU-brief Questionnaire Results and Changes from Baseline

### 12.6.3.2.3 Modified Cigarette Evaluation Questionnaire

The mCEQ will be administered daily from Days -1 to 5, and Days 30 Visit, 60 Visit and 90 Visit. All summaries, profiles and analysis will be presented for the THS 2.2 Menthol and mCC only. The mCEQ is not captured for the SA arm.

The domain scores, along with the percent change from baseline will be summarized. The answers to the individual questions, along with the domain scores, changes and percent changes from Baseline will be listed.

The profiles of the raw means from baseline to Day 90 for the five subscale scores will be produced.

The analysis will be performed separately for each post-baseline timepoint in the subscales. An ANCOVA model will be used with terms for baseline mCEQ score, sex, and average daily mCC consumption over the last 4 weeks as reported during screening, and randomization arm. No adjustment will be made for multiple comparisons.

The SAS code to be used is similar to the model reported in Section 12.6.1.3 "Sensitivity Analysis".

LS means for each product along with the difference (THS 2.2 Menthol - mCC) with 95% CI will be presented in the tables.

All figures, summaries and analyses will be performed on the PP Set and the FAS.

The data will be presented in the below outputs:

TFL number	Title
FIGURES	
15.1.2.6.1	MCEQ Subscales Arithmetic Mean and 95% CI – PP Set
15.1.2.6.2	MCEQ Subscales Arithmetic Mean and 95% CI – FAS
15.1.2.7.1	MCEQ Subscales Least Squares Means Differences and 95% CI – PP Set
15.1.2.7.2	MCEQ Subscales Least Squares Means Differences and 95% CI – FAS
TABLES	
15.2.4.54.1	Descriptive Statistics of MCEQ Subscales – PP Set
15.2.4.54.2	Descriptive Statistics of MCEQ Subscales – FAS
15.2.4.55.1	Analysis of MCEQ Subscales – PP Set
15.2.4.55.2	Analysis of MCEQ Subscales – FAS
LISTINGS	
15.3.6.16	Listing of MCEQ Questionnaire Results and Changes from Baseline

#### 12.6.3.2.4 Minnesota Nicotine Withdrawal Questionnaire

The MNWS will be administered daily from Days 0 to 6, and Days 31, 61 and 91 for the assessment of Day-1 to Day 5, and Days 30, 60 and 90 as it is a 24-hour recall questionnaire.

All summaries, profiles and analysis will be presented for the THS 2.2 Menthol, mCC and SA arms.

The total score, along with the percent change from baseline will be summarized. The answers to the individual questions, along with the total score, the changes and percent changes from baseline will be listed.

The profiles of the raw means from baseline to Day 90 for the total scores will be plotted.

The analysis will compare each post baseline timpoint separately for the total score. An ANCOVA model will be used with terms for baseline score, sex, average daily mCC consumption over the last 4 weeks as reported during screening, and randomization arm,. No adjustment will be made for multiple comparisons.

The SAS code to be used is similar to the model reported in Section 12.6.1.3 "Sensitivity Analysis".

LS means for each product along with the difference (THS 2.2 Menthol - mCC) and (THS 2.2 Menthol – SA) with 95% CI will be presented in the tables.

All figures, summaries and analyses will be performed on the PP Set and FAS only.

The data will be presented in the below outputs:

TFL number	Title
FIGURES	
15.1.2.8.1	MNWS Total Score Arithmetic Mean and 95% CI – PP Set
15.1.2.8.2	MNWS Total Score Arithmetic Mean and 95% CI – FAS
15.1.2.9.1	MNWS Total Score Arithmetic Least Squares Means and 95% CI – PP Set
15.1.2.9.2	MNWS Total Score Arithmetic Least Squares Means and 95% CI – FAS
TABLES	
15.2.4.56.1	Descriptive Statistics of MNWS Total Score – PP Set
15.2.4.56.2	Descriptive Statistics of MNWS Total Score – FAS
15.2.4.57.1	Analysis of MNWS Total Score – PP Set
15.2.4.57.2	Analysis of MNWS Total Score – FAS
LISTINGS	
15.3.6.15	Listing of MNWS Questionnaire Results and Changes from Baseline

### **12.6.3.2.5 Human Smoking Topography Questionnaire**

The HST questionnaire will be administered on Days 0, 4, 30, 60 and 90.

The number and percentage of subjects in each category of the items of the questionnaire will be summarized. The individual responses will be listed.

All summaries will be performed on the PP Set.

The data will be presented in the below outputs:

---

**TFL number Title**

---

**TABLES**

15.2.4.58 Descriptive Statistics of HST Questionnaire Data – PP Set

**LISTINGS**15.3.7.2 Listing of HST Questionnaire Results

---

### **12.6.3.2.6 Risk Factor Surveillance System Questionnaire**

The Risk Factor Surveillance System Questionnaire will be administered on Day -1 and Day 5.

The individual responses will be listed only.

The data will be presented in the below outputs:

---

**TFL number Title**

---

**LISTINGS**15.3.6.17 Listing of Risk Factor Surveillance System Questionnaire Results

---

### **12.6.3.2.7 Smoking Questionnaire and Supplemental Questions**

The SQ and supplemental questions will be administered on Days -1 and 5.

The individual responses will be listed only.

The data will be presented in the below outputs:

---

**TFL number Title**

---

**LISTINGS**15.3.6.18 Listing of Smoking Questionnaire and Supplemental Questions Results

---

### 12.6.3.2.8 Prochaska 'Stage of Change' Questionnaire

The Prochaska 'stage of change' questionnaire will be administered at Screening, Day -2, Day 30, Day 60 and Day 90.

The Prochaska 'Stage of Change' Questionnaire Results will be summarized on the FAS and Compliant Population. The individual responses will be listed.

The data will be presented in the below outputs:

TFL number	Title
TABLES	
15.2.4.59.1	Descriptive Statistics of Prochaska 'Stage of Change' Questionnaire Results – FAS
15.2.4.59.2	Descriptive Statistics of Prochaska 'Stage of Change' Questionnaire Results – Compliant Population
LISTINGS	
15.3.6.19	Listing of Prochaska 'Stage of Change' Questionnaire Results

### 12.6.3.3 Human Smoking Topography Parameters

The HST assessments will take place on Day 0, Day 1, Day 4, Day 30, Day 60 and Day 90 in the THS 2.2 Menthol and mCC arms only, if mCC are compatible with the HST SODIM® device. On Day 0, Day 1 and Day 4 the HST will be conducted on each product use. On Day 30, Day 60 and Day 90 the HST will be recorded over a 4-hour period only.

The per puff parameters are shown in **Table 13** and the per cigarette parameters are shown in **Table 14**.

The per-cigarette parameters derived from the HST assessments will be averaged per day and summarized along with their changes from baseline. The per-puff and per-cigarette parameters will be listed. In addition the randomization arm mean and 95% CI per cigarette parameters will be presented graphically.

The averaged per-cigarette parameters will be analysed on Days 1, 4, 30, 60 and 90 separately using an ANCOVA model with terms for baseline score, sex, average daily mCC consumption over the last 4 weeks as reported during screening and randomization arm. No adjustment will be made for multiple comparisons.

The SAS code to be used is similar to the model reported in Section 12.6.1.3 "Sensitivity Analysis".

LS means for each product along with the ratio (THS 2.2 Menthol : mCC) and 95% CI will be presented in the tables.

All figures, summaries and analyses will be performed on the PP Set only.

The data will be presented in the below outputs:

TFL number	Title
FIGURES	
15.1.2.10	HST Parameters Averaged Over the Visit Arithmetic Mean and 95% CI – PP Set
TABLES	
15.2.4.60	Descriptive Statistics of HST Parameters per Cigarette – PP Set
15.2.4.61	Analysis of HST Parameters per Cigarette – PP Set
LISTINGS	
15.3.7.1	Listing of HST Assessments and Changes from Baseline

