7.8.2 Human Smoking Topography Assessment

Human smoking topography involves the measurement of each smoker's unique way of smoking mCCs or using Menthol Tobacco Sticks using the HST SODIM® portable device. The HST SODIM® device, model SPA/M (SODIM® Instrumentation, Fleury les Aubrais, France) is a device which is used to measure smoking topography (Appendix 4). It consists of a special sample holder (containing a constriction in the middle) which is placed between the smoker's mouth and the filter of the mCC or Menthol Tobacco Stick being smoked/used. The holder is connected by two narrow tubes to a portable data logger/recording system (Appendix 4 for a description of the device).

At Day 0, the HST SODIM® device has to be used for all mCC smoked for all subjects. On Day 1 and Day 4 of the confinement period, the HST SODIM® device has to be used for every smoking event for all subjects in the mCC and THS 2.2 Menthol arms. On Day 30 Visit (Day 30), Day 60 Visit (Day 60), and Day 90 Visit (Day 90) of the ambulatory period, HST assessment will start between 08:30 and 09:30 AM with 4 hours recording. Smoking topography with the HST SODIM® device will **not** be done in subjects smoking mCC that are incompatible with the HST SODIM® device (e.g., slim mCC). For subjects in the SA arm, no HST assessments will be performed.

For each subject, one HST SODIM® device will be assigned at Day -1, which will be used by that subject on all HST assessment days (in the case of malfunction, the device will be exchanged). HST SODIM® devices will be assigned to all subjects smoking mCCs which are compatible with the HST SODIM® device at each cohort according to the screening number.

The Sponsor will provide training on the use of the HST SODIM® device to the study site staff. The study site staff will, in turn, provide training to the subjects. All HST SODIM® devices will be returned to the Sponsor after completion of the study.

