Data and information contained in this document are considered to constitute trade secrets and confidential commercial information, and the legal protections provided to such trade secrets and confidential information are hereby claimed under the provisions of United States law. No part of this document may be publicly disclosed without the written consent of Philip Morris International.

Time of Discharge from
confinement-/beginning of
the ambulatory exposure
period

Abbreviations: 8-epi-PGF2 α = 8-epi-prostaglandine F2 α ; 11-DTX-B2 = 11-dehydro-thromboxane B2; AE = adverse event; BMI = body mass index; BoExp = biomarkers of exposure; BP = blood pressure; mCC = menthol conventional cigarette(s); CO = carbon monoxide; CYP = cytochrome P450 enzyme; ECG = electrocardiogram; MNWS = Minnesota Nicotine /Withdrawal Scale; PK = pharmacokinetics; SA = smoking abstinence; SAE = serious adverse event; sICAM-1 = soluble inter-cellular adhesion molecule; WBC = white blood cell count.

9.3 Ambulatory Period (from time of Discharge on Day 6 to Day 90 Visit)

For Day 30 Visit (Day 30 and Day 31), Day 60 Visit (Day 60 and Day 61), and Day 90 Visit (Day 90 and Day 91), a time window of +/- 5 days will be allowed with respect to Day 6, Day 30 Visit and Day 60 Visit respectively. The time of opening and end of the visit are given as an estimate.

Table 17 shows the assessments that will be performed on Day 30 Visit and Day 60 Visit of the ambulatory period:

Table 17. Time Schedule – Day 30 Visit and Day 60 Visit (from the time of check-in in the morning prior to 08:30 AM to check-out of the subject on the day after)

Time	Blood sample	Procedures	Additional information
Start of procedure		Day 30 and Day 60	
In the morning prior to 08:30 AM		Opening of the Day 30 Visit and Day 60 Visit	No product restriction prior to the opening of the visit
			Product use will be allowed on site in the THS 2.2 Menthol and mCC arms from the time of check-in in the morning to around 11:00 PM.
			The use of THS 2.2 menthol in smokers allocated to mCC and SA arms will be forbidden
		Support for smoking abstinence (SA arm only) if needed	At any time of the day
		AE/SAE questioning; Concomitant medication	At any time during the day

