	Day 30 and Day 60	10:00 AM-11:30 AM irrespective of product use
	Day 90	10:00 AM-12:30 PM irrespective of product use
COHb blood sampling	Days -1 to 4	08:00 PM to 09:30 PM
	Morning sample on Day 5	Within 15 minutes prior to product use (for THS 2.2 Menthol and mCC arms) or between 08:00 AM and 09:30 AM (SA arm)
	Day 5 other samples	Between 12:00 PM and 01:30 PM, 04:00 PM and 05:30 PM, and 08:00 PM and 09:30 PM
	Day 30 and Day 60	Irrespective of product use between 10:00 AM and 11:30 AM.
	Day 90	Irrespective of product use

Assessment	Nominal Time point(s)	Window
Oxysterols and Blood sampling for bio-banking for transcriptomics	day 0, day 6 and Day 91	between 10:00 AM and 12:30 AM. Has to be done after at least 10 hours of fasting.
Nasal Epithelial Collection and Buccal Collection	Day 0 and Day 90	In the afternoon before 9:00 PM. Subject must not have eaten at least 30 minutes prior to collection
	Day 6	Prior to discharge. Subject must not have eaten at least 30 minutes prior to collection
HST Questionnaire	Day 0 Day 4, Day 30, Day 60 and Day 90 for all subjects in the THS 2.2 Menthol and mCC arms	08:00 PM-11:00 PM 08:00 PM-09:30 PM
HST Recording	Day 0 Day 1 and Day 4 for all subjects in the THS 2.2 Menthol and mCC arms smoking compatible mCC Day 30, Day 60 and Day 90 for all subjects in the THS 2.2 Menthol and mCC arms smoking compatible mCC	06:30 AM-11:00 PM 06:30 AM-11:00 PM Start time: 08:30 AM to 09:30 AM. End time: 12:30 PM to 01:30 PM. 4-hour recordings ± 15 min
Ambulatory Visit	Day 30, Day 60 and Day 90 Visits	± 5 days.

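### Topography changes from baseline at Days 30, 60 and 90 set a 4-hour window against a full-day Day 0 average, so any time-of-day pattern is mixed with time on product

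*SAP*

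**What the plan says.** SAP 12.6.3.3 sets two recording schemes. For baseline and confinement: "On Day 0, Day 1 and Day 4 the HST will be conducted on each product use". SAP Table 23 gives the clock window for those days as "06:30 AM-11:00 PM", and Protocol 7.8.2 confirms the baseline rule: "At Day 0, the HST SODIM® device has to be used for all mCC smoked for all subjects". For the ambulatory visits: "On Day 30, Day 60 and Day 90 the HST will be recorded over a 4-hour period only". Table 23 gives "Start time: 08:30 AM to 09:30 AM. End time: 12:30 PM to 01:30 PM. 4-hour recordings ± 15 min", and Protocol 7.8.2 agrees: "HST assessment will start between 08:30 and 09:30 AM with 4 hours recording".

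The analysis then treats the days alike: "The per-cigarette parameters derived from the HST assessments will be averaged per day and summarized along with their changes from baseline". A separate ANCOVA on each of Days 1, 4, 30, 60 and 90 adjusts for baseline and reports the THS 2.2 Menthol to mCC ratio. Figure 15.1.2.10 plots the values averaged over each visit.

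SAP Table 26 defines baseline in general terms, and the text below it says that any exception will be given in the relevant section. Section 12.6.3.3 gives none, so the HST baseline is the full-day Day 0 average.

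Product use before the recording also differs. On Day 0, smoking is held until the CYP2A6 sample, the questionnaires and full lung function are done (Protocol 4.1 and 6.2.2). For the ambulatory visits, Protocol 9.3, Tables 17 and 18, says "No product restriction prior to the opening of the visit".

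**The concern.** The exploratory objective (Protocol 3.3 and 3.4.3, SAP 5.3) is to describe puffing through the study in switchers, compared with smokers who continue mCC. The step from Days 0, 1 and 4 to Days 30, 60 and 90 carries the information on how puffing develops with longer use. It coincides exactly with the change from full-day to 4-hour recording. If people puff differently in the late morning than over the whole day, that difference appears as a change over time in both arms and cannot be told apart from adaptation to the product.

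Elsewhere the SAP does match clock time. A missing Day 5 evening COHb is replaced by the Day 4 evening value even when other Day 5 values exist (12.1.5), and confinement nicotine and cotinine use evening values with an evening baseline (12.6.2.2). HST has no such rule.

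**Working it through.** **Inputs.** Recording windows from SAP Table 23. Averaging, change from baseline and model from SAP 12.6.3.3. The documents give no within-day topography data, so the illustration in steps 3 to 5 rests on assumptions.

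**1. The plan's own figure.** 08:30 AM to 12:30 PM and 09:30 AM to 01:30 PM are each 4.0 h, which reproduces the stated 4-hour recording.

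**2. Coverage.** 06:30 AM to 11:00 PM is 16.5 h. 4/16.5 = 24.2%; with the ± 15 min tolerance, 3.75/16.5 = 22.7% to 4.25/16.5 = 25.8%. Day 0 is somewhat shorter than 16.5 h because of the morning hold. With use spread evenly, the window holds 10 × 4/16.5 = 2.4 products for a 10-per-day smoker and 20 × 4/16.5 = 4.8 for a 20-per-day smoker.

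**3. Effect on the change from baseline (illustration).** Let the per-cigarette level in the window be (1 + s) times the rest-of-day level, with even use, f = 4/16.5, no effect of time on product, and an assumed true product effect of +20%.

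- mCC: apparent change = (1 + s) / [f(1 + s) + (1 − f)] − 1
- THS: apparent change = 1.20 × (1 + s) / [f(1 + s) + (1 − f)] − 1

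For s = 10%: 1.10 / (0.2424 × 1.10 + 0.7576) − 1 = 1.10/1.0242 − 1 = 7.4%. For THS, 1.20 × 1.074 − 1 = 28.9%.

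| Assumed s | mCC change (true 0%) | THS change (true +20%) | THS:mCC ratio |
|---|---|---|---|
| 0% | 0.0% | +20.0% | 1.20 |
| 5% | +3.7% | +24.5% | 1.20 |
| 10% | +7.4% | +28.9% | 1.20 |
| 20% | +14.5% | +37.3% | 1.20 |

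A lower level in the window would push the changes the other way.

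**4. Effect on the ANCOVA.** 3,000 simulated trials per value of s were run with 40 subjects per arm and assumed log-scale SDs (0.30 between subjects, 0.10 baseline error, 0.15 outcome error). The mean THS:mCC ratio was 1.198, 1.201 and 1.200 for s of 0%, 10% and 20%. The shared window cancels.

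**5. With a window-matched Day 0 value.** The mCC change becomes (1 + s)/(1 + s) − 1 = 0%, and the THS change 1.20 − 1 = +20%, for every s.

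**The case against.** The full objective compares the two product arms, and the only planned inference is the same-day ratio, where both arms share the window. The mCC arm shows any common time-of-day shift without a product switch, so a reader who compares the two arms' changes can largely remove it. The parameters are per-cigarette averages, so a shorter recording does not by itself move them; 24% is coverage, not bias. The window difference is openly prespecified, and the endpoint is exploratory. All of this stands and limits the reach of the point. It does not make the within-arm changes or the plotted time course comparable across the two schemes, and the SAP plans to report both.

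A windowed baseline has its own weakness. On Day 0, cigarettes in that window follow the smoking hold and full lung function testing. Days 30 and 60 have no lung function testing, and at the Day 90 Visit it falls on Day 91, after the recording. Few Day 0 cigarettes may remain. This is a good reason not to replace the prespecified ANCOVA covariate. It applies far less to Days 1 and 4, when product use starts at 06:30 AM with no lung function testing.

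A reader might go further and drop the first use of the day from the windowed values. The documents do not support this. Use before ambulatory check-in is captured as daily numbers in the diary (Protocol 6.5.4), with no clock times described, so nobody can tell whether the first recorded use was the first that day. The exclusion could not be applied equally on both sides.

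**Conclusion.** The point holds for the within-arm changes from baseline at Days 30, 60 and 90 and for the trend from Days 1 and 4 to those visits. Both mix any time-of-day pattern with time on product. The size is unknown; the 3.7% to 14.5% for mCC above follows from assumed window differences of 5% to 20% and even use.

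Two stronger readings are tempting. A reader might infer that the THS:mCC ratio at the ambulatory visits is biased. It is not, unless the within-day pattern differs by product, and the documents give no evidence on that; the ratio simply describes the 4-hour window. A reader might also infer that the full-day covariate costs precision. It is less closely matched to the outcome, but no loss has been shown, and a windowed covariate resting on very few cigarettes could be noisier. No primary or secondary endpoint is affected. Impact is low.

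**What to change.** In SAP 12.6.3.3:

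- Add Day 0, Day 1 and Day 4 summaries restricted to the ambulatory clock window (4 hours, start 08:30 to 09:30 AM), with the rule for the start time within that hour fixed in advance.
- Report the Day 30, 60 and 90 changes against the windowed Day 0 value, and plot the windowed Day 0, 1 and 4 values beside the ambulatory visits.
- Keep the prespecified full-day baseline as the ANCOVA covariate. Use the windowed covariate as a sensitivity analysis only.
- Do not exclude the first use of the day.
- State in the outputs that Day 0 smoking was withheld until the morning procedures were done, so the windowed Day 0 value may rest on few cigarettes and Days 1 and 4 are the cleaner comparators. Protocol 7.4.11.1 includes bronchodilator spirometry among those procedures, whereas SAP 12.6.4.4.4 describes spirometry after Screening as done without bronchodilator; the two must be reconciled before the note is worded.

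The cost is SAP wording and one derivation. No new data are needed: every use on those days is recorded, and Protocol 6.5.1 logs dispense and return times for each product in confinement. The downside is fewer cigarettes per subject, and so noisier windowed means.
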